### 10.2 Primary Efficacy Endpoint

#### 10.2.1 Primary Analysis

The primary endpoint is the aggregated average of change from baseline-RT in number of nocturnal voids after 12 weeks of treatment, that is, averaged across all post-randomization visits. The objectives of the primary analysis are to establish Proof-of-Concept of FE 201836 and to estimate the dose-response profile of FE 201836. The analyses will be performed on the ITT-RT analysis set.

The overall trial outcome is proof-of-concept evaluated by the posterior probability that 500 µg FE 201836 has superior efficacy as compared to placebo ( $Pr(\mu_{500} < \mu_{Plb}) > 97.5\%$ ) based on a Bayesian analysis of the dose-response profile at Week 12 for the ITT-RT analysis set not including the active comparator desmopressin.

The dose-response profile will be characterized by the posterior estimates of the mean dose-response at each dose,  $\mu_d$ , corresponding to two nocturnal voids at baseline and the mean dose-response contrast versus placebo,  $\Delta_d$ , with their associated 95% credibility intervals. The posterior probabilities  $Pr(\Delta_d < -0.3)$ ,  $Pr(\text{dose } d \text{ is MED})$ , and  $Pr(\text{dose } d \text{ is ED}_{85})$ , will be tabulated. The dose-response curve relative to placebo will also be presented graphically with its 95% credible interval in the plots illustrating the therapeutic window (Section 10.4). No multiplicity adjustment will be performed.

The dose-response profiles are determined using the following model: Let  $x_{t,i}$  denote the observed cross-sectional change from baseline-RT in nocturnal voids (averaged across the nights in the Voiding diary corresponding to the visit) and let  $y_{t,i}$  denote the aggregated average change from baseline for subject  $i$ , averaged across post-randomization visits up to time  $t$  (for visit windows see Section 3.1.5):

$$y_{t,i} = \frac{\sum_{k=1}^t x_{k,i}}{t}, \quad t = 1, 2, 3, 4,$$

where  $t$  denotes the nominal post-randomization time points reflecting Visits 5, 6, 7 and 8, corresponding to Weeks 1, 4, 8, and 12, respectively. The final endpoint,  $y_{4,i}$  is modelled as being an observation of

$$Y_{4,i} \sim N(\beta \cdot (x_{0,i} - 2) + \mu_d, \sigma^2), \quad (1)$$

where  $x_{0,i}$  is the baseline-RT number of nocturnal voids,  $\sigma^2$  is the error variance, and  $\mu_d$  describes the dose-response relationship.  $\mu_d$  is assumed to follow a four-parameter sigmoidal model:

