**Table 5 Analysis of Endpoints**

Endpoint	Analysis category				
	Bayesian Estimation of Dose-response Curve for Aggregated Averages	MMRM	Repeated logistic regression (Generalized Estimating Equation [GEE])	ANCOVA	Correlation Analysis
Efficacy Endpoints					
Aggregated average change from baseline during the 12 weeks randomized-treatment period for number of nocturnal voids	Primary	Sensitivity, Therapeutic Window			
Change from baseline in number of nocturnal voids at the visit a		Secondary			
Rate of response defined as 50% reduction in nocturnal voids from baseline based on aggregated average change from baseline	Secondary		Secondary		
Rate of response defined as 50% reduction in nocturnal voids from baseline a			Secondary		
Rate of response defined as 33%, 60%, 70%, 80%, 90% and 100% reduction from baseline in number of nocturnal voids a			Explorative		
Rate of response defined as 1, 2, and 3 voids reduction from baseline in number of nocturnal voids a			Explorative		
Percentage of nights during treatment period with at most one nocturnal void b				Secondary	
Percentage of nights during treatment period with complete response b				Secondary	
Change from baseline in NUV c	Secondary	Secondary			
Change from baseline in FUSP a	Secondary	Secondary			Explorative d
Change from baseline in total sleep time per night a		Explorative			
Change from baseline in nocturnal diuresis rate (hourly) c		Secondary			
Change from baseline in NPi c		Explorative			
Change from baseline in NI Diary Total Score a	Secondary	Secondary			
Change from baseline in NI Diary Overall Impact Score a	Secondary	Secondary			

Endpoint	Analysis category				
	Bayesian Estimation of Dose-response Curve for Aggregated Averages	MMRM	Repeated logistic regression (Generalized Estimating Equation [GEE])	ANCOVA	Correlation Analysis
PGI-I urinary symptoms score a, e		Secondary			
Change from baseline in PGI-S score a		Secondary			
Change from baseline in Bother as measured by the Hsu 5-point Likert Bother Scale a		Secondary			
Change from baseline in ISI f		Secondary			
Copeptin levels at Visit 2 g					Explorative
Change from baseline in copeptin levels h					Explorative
Safety Endpoints					
Change from baseline in mean 24-hour urine volume c		Safety			

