### 10.3.2 Scoring of Patient-Reported Outcomes

The post-randomization, visit-specific, cross-sectional change from baseline-RT,  $x_{t,i}$ , in number of nocturnal voids is defined as the average across the nights in the Voiding Diary corresponding to the single visit. Regarding assigning number of voids for a single night, the following rules are used:

1. Voids less than 5 minutes apart will be collapsed into a single void and the corresponding volumes will be summed to a total volume. Voids on different sides of a time threshold (5 minutes after bed time with the intention to sleep at night, rising in the morning, and 30 minutes after rising in the morning) will not be collapsed.
2. If day/night cannot be assigned due to missing go-to-bed or got-up time, number of nocturnal voids and NUV for that 24-hour period is set to missing.
3. If day/night can be assigned and there are no voids during the night period, number of nocturnal voids is set to 0 for that 24-hour period and NUV is set to 0 plus the volume of the first void within 30 minutes of rising in the morning.
4. If day/night can be assigned, and there are a positive number of voids during both the night period, the number of voids during the night period is used, whether or not the volume of every void is registered. If at least one volume is not registered, NUV is set to missing for that 24-hour period.

The post-randomization aggregated average change from baseline-RT,  $y_{t,i}$ , in number of nocturnal voids is defined as the average of the cross-sectional changes from baseline-RT,  $x_{s,i}$ , across the post-randomization visits up to and including the current visit. If the cross-sectional change from baseline-RT,  $x_{t,i}$ , is missing at a single visit, the corresponding aggregated average change from baseline-RT,  $y_{t,i}$ , will be set to missing.

The aggregated average change from baseline being less or equal to 50% of the baseline-RT number of nocturnal voids,  $z_{50\%,t,i}$ , is derived from the corresponding aggregated average change from baseline in number of nocturnal voids,  $y_{t,i}$ , as  $z_{50\%,t,i} = 1$  if  $y_{t,i}/x_{0,i} \leq -0.5$ , and  $z_{50\%,t,i} = 0$  otherwise.

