The visit-specific, cross-sectional responder variables related to number of nocturnal voids (33%, 50%, 60%, 70%, 80%, and 90% reduction from baseline; and 1, 2, and 3 voids reduction from baseline) are derived by categorization of the corresponding  $x_{t,i}$  divided by the baseline-RT number of nocturnal voids,  $x_{0,i}$ .

The percentages of nights with response defined as at most one nocturnal void and complete response (no nocturnal voids), respectively, are derived as the percentage of nights with the specific response among all single, post-randomization nights in the Voiding Diary for which number of nocturnal voids can be derived.

The NUV for a single night is the total urine volume in mL from 5 minutes after bedtime with the intention to sleep including the first void within 30 minutes of rising in the morning. The NUV for a visit is calculated as the average of the single-night values. Aggregated values are derived similarly to the derivation of the aggregated values for number of nocturnal voids.

The FUSP for a single night is calculated as the time in minutes from the time of going to bed to the time of first nocturnal void, or time of awakening if no void occurred. The FUSP for a visit is calculated as the average of the single-night values. Aggregated values are derived similarly to the derivation of the aggregated values for number of nocturnal voids.

The total sleep for a single night is calculated as the time in minutes from the time of going to bed to the time of awakening. The total sleep for a visit is calculated as the average of the single-night values.

The diuresis rate measured in mL/min for a single night is calculated as NUV/total sleep. The diuresis rate for a visit is calculated as the average of the single-night values.

The NPi for a single night is calculated as  $100\% \cdot \text{NUV}/24\text{-hours urine volume}$ . The NPi for a visit is calculated as the average of the single-night values.

The NI Diary outcomes will be scored as described in [Holm-Larsen \(2014\)](#):

The NI Diary Total Score for a single night will be calculated as the sum of the scores for the first 11 questions divided by 44 and multiplied by 100. If any of the single-item scores is missing, the NI Diary Total Score is missing for that single night. The NI Diary Total Score for a visit is calculated as the average of the single-night values. The number of nights on which the NI Diary Total Score for a visit is based will be provided.

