#### **10.3.5 Treatment effects on cross-sectional binary variables**

Binary endpoints such as the cross-sectional “responder status” at a visit will be analysed using SAS PROC GENMOD with logit as the link function for the responder probability. An unstructured correlation matrix will be used as working correlation matrix if technically possible, alternatively an autoregressive, a compound-symmetry, or if necessary, an independent working correlation matrix will be used. The systematic effects will include visit and treatment-by-visit interaction as factors and will be adjusted for the  $\log_2$ -transformed number of nocturnal voids at baseline-RT, subtracted by 1, as a covariate interacting with visit number. Odds ratios relative to placebo with associated 95% confidence intervals (without multiplicity adjustment) will be presented. The analyses will be applied to the observed data for the ITT-RT analysis set. Combinations of visit and dose of FE 201836 where all or none of the subjects respond will be omitted from the analysis since this corresponds to estimates of infinity in a logistic regression model.

For the investigation of interaction with sex, combinations of sex, visit and dose of FE 201836 where all or none of the subjects respond will be omitted from the analyses, and an autoregressive correlation matrix will be used, if technically possible, alternatively, a compound-symmetry, or if necessary, an independent working correlation matrix will be used.

In the analysis of the responder variable corresponding to one nocturnal void decrease from baseline, only subjects with at least one nocturnal void at baseline will be included. In the analysis of the responder variable corresponding to two nocturnal voids decrease from baseline, only subjects with at least two nocturnal voids at baseline will be included. In the analysis of the responder variable corresponding to three nocturnal voids decrease from baseline, only subjects with at least three nocturnal voids at baseline will be included.

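### The SAP derives the exploratory 1-, 2- and 3-void responder variables from the relative change, although an absolute change is clearly intended

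*SAP*

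**What the plan says.** SAP Section 10.3.2 covers the visit-specific responder variables in a single sentence. It first lists the percentage levels from 33% to 90% and then runs on: "and 1, 2, and 3 voids reduction from baseline) are derived by categorization of the corresponding". For every variable in that list, the quantity to be categorized is the same: x_t,i "divided by the baseline-RT number of nocturnal voids". The same section introduces x_t,i as "The post-randomization, visit-specific, cross-sectional change from baseline-RT", averaged over the diary nights of the visit. Section 10.2.1 states that x_0,i "is the baseline-RT number of nocturnal voids". No cut-offs are given for these variables. By contrast, Section 10.3.2 does give an explicit cut for the aggregated 50% responder: y_t,i / x_0,i at or below -0.5.

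Three other places bear on the point:

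- SAP Section 2.2 lists reductions of 1, 2 and 3 voids as exploratory endpoints, separately from the percentage reductions.
- SAP Section 10.3.5 restricts each void-count analysis by baseline. The rule for two voids reads: "responder variable corresponding to two nocturnal voids decrease from baseline, only subjects with at least two nocturnal voids at baseline will be included". There are matching rules for one and three voids.
- SAP Table 5 plans an exploratory GEE analysis for "Rate of response defined as 33%, 60%, 70%, 80%, 90% and 100% reduction from baseline in number of nocturnal voids". The 100% level is missing from the Section 10.3.2 list.

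SAP Section 14, on deviations from the protocol, takes up neither the division nor the missing 100% level.

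**The concern.** A reduction of k voids is an absolute quantity. Dividing the change by baseline gives a proportion, and cutting a proportion at 1, 2 or 3 does not identify subjects who lost 1, 2 or 3 voids. A programmer who follows Section 10.3.2 as written would produce one variable that repeats another endpoint and two that are empty. Section 10.3.5 then drops any combination of visit and FE 201836 dose in which nobody responds, so the 2- and 3-void models would have no active-dose cells left.

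The absolute-reduction endpoints also have an interpretive use. The exit interview protocol (protocol Appendix 1) asks subjects what reduction in nocturnal voids is meaningful to them and aims to map the answers back to the trial data. Responder rates on the void scale are the natural counterpart.

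**Working it through.** No sample size, power or error rate depends on this point, so there is no plan figure to reproduce. The check is of what the stated rule can yield.

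**Inputs**

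- x_t,i is the change from baseline-RT in the visit average (SAP 10.3.2), and x_0,i is the baseline-RT count (SAP 10.2.1).
- The lowest nightly count is zero. With no voids in the night period, "number of nocturnal voids is set to 0 for that 24-hour period" (SAP 10.3.2).
- Eligibility requires x_0,i of at least 2 at Visit 4 (protocol 4.1.1, criterion 10), so the divisor is positive.
- Assumption: literal cuts of -1, -2 and -3 on the ratio, since the SAP states none.

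**Bound**

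Let p be the visit average, with p ≥ 0. Then x_t,i = p − x_0,i ≥ −x_0,i, so x_t,i / x_0,i ≥ −1, with equality only when p = 0. Therefore:

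- ratio ≤ −1 requires p = 0, which is exactly a 100% reduction at the visit;
- ratio ≤ −2 and ratio ≤ −3 cannot occur at any baseline.

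**Examples**

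| Baseline | Visit average | Change | Ratio | Absolute scale | Literal ratio rule |
|---|---|---|---|---|---|
| 3 | 2 | −1 | −0.333 | 1-void responder | none |
| 3 | 1.5 | −1.5 | −0.5 | 1-void responder | none |
| 4 | 2 | −2 | −0.5 | 1- and 2-void responder | none |
| 4 | 1 | −3 | −0.75 | 1-, 2- and 3-void responder | none |
| 3 | 0 | −3 | −1 | 1-, 2- and 3-void responder | 1-void only |

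**Enumeration**

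Take baselines from 2 to 6 and visit averages from 0 to 8, both in steps of 1/3 because they are 3-night averages. The upper limits are assumptions. This gives 13 × 25 = 325 cells.

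| Response | Literal: x/x_0 ≤ −k | Absolute: x ≤ −k |
|---|---|---|
| 1 void | 13 (all with visit average 0) | 130 |
| 2 voids | 0 | 91 |
| 3 voids | 0 | 55 |

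The 13 literal 1-void cells are the same 13 cells that meet a 100% reduction. The absolute counts follow directly. At baseline m/3, with m from 6 to 18, the number of qualifying visit averages is m − 2 for one void (4 + … + 16 = 130), m − 5 for two (1 + … + 13 = 91), and m − 8 for three where m ≥ 9 (1 + … + 10 = 55). These counts show what is attainable. They are not expected response rates.

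**Consistency with Section 10.3.5**

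On the absolute scale, a subject needs at least k voids at baseline to be able to lose k, so the baseline restriction removes exactly those who could never respond. All 55 three-void cells above sit at baselines of 3 or more. On the ratio scale the restriction has no purpose, because the bound of −1 is the same at every baseline.

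**The case against.** The strongest reply is that the intent is not in doubt. Section 2.2 names the endpoints as numbers of voids, and the baseline restriction in Section 10.3.5 makes sense only for an absolute change. Section 10.3.2 also gives no threshold, so the cuts of -1, -2 and -3 on the ratio are supplied by the reader. A subject-specific cut of −k / x_0,i applied to the same ratio is equivalent to x_t,i ≤ −k and would give the right variable. Moreover, an empty 2- or 3-void table would be noticed on the first run. Only the 1-void variable could yield a plausible but wrong table.

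Much of this stands. The intent is recoverable, and the empty-cell result is conditional on the literal cuts. What does not stand is that the sentence is therefore adequate. It names a specific quantity to categorize, that quantity is wrong for three of the listed variables, no formula elsewhere in the SAP overrides it, and the subject-specific cut that would rescue it is not stated.

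A reader might go further and infer any of the following, which the documents do not support:

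- *That the trial's 2- and 3-void results will be empty.* This needs cut-offs that the SAP does not give, and it needs a programmer to disregard Sections 2.2 and 10.3.5.
- *That the 1-void variable would duplicate complete response.* In the SAP that term is a percentage of nights without voids, analysed by ANCOVA. The overlap is with the visit-level 100% responder.
- *That the 100% responder is undefined.* Its absence from the list is an omission, but a 100% reduction has only one meaning: a visit average of zero.

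**Conclusion.** The derivation is wrong as written for the 1-, 2- and 3-void responders and conflicts with SAP Sections 2.2 and 10.3.5. Under literal cuts of -1, -2 and -3, the 1-void variable collapses onto the 100% responder, the other two have 0 responders in every arm at every visit, and all their FE 201836 cells would be omitted. That size rests on the assumed cuts; the lower bound of −1 on the ratio does not.

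The point is minor. Three of the nine exploratory responder definitions (33, 60, 70, 80, 90 and 100%, plus 1, 2 and 3 voids) are affected, and a fourth, 100%, is merely missing from a list. The primary analysis, the visit-specific and aggregated 50% responder endpoints, and the operating characteristics are untouched, because the ratio is the right quantity for a percentage and none of the others uses this sentence.

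**What to change.** Split the sentence in SAP Section 10.3.2 and state the cuts:

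- 33%, 50%, 60%, 70%, 80%, 90% and 100% response: x_t,i / x_0,i at or below −0.33, −0.5, −0.6, −0.7, −0.8, −0.9 and −1 respectively.
- 1-, 2- and 3-void response: x_t,i at or below −1, −2 and −3, without division.

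Adding 100% is for completeness. The baseline restrictions in Section 10.3.5 can stay as they are, since they already fit the absolute scale. The cost is one sentence, with no change to data collection, to the models or to any other endpoint. It is best made before unblinding, so that the choice is documented in the SAP and not left to the programming.

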### 10.3.3 Bayesian estimation of the sigmoidal dose-response curve

Bayesian estimation of the sigmoidal dose-response curve for aggregated, quantitative outcomes will follow the approach described for the primary analysis in Section 10.2.1 using the priors  $\beta \sim N(0, 10^2)$ ;  $\alpha_1, \alpha_2 \sim N(\bar{a}, 5^2)$  with the outcome-specific mean  $\bar{a}$  presented in [Table 6](#);  $\alpha_3 \sim N^+(2, 10^2)$ ;  $\alpha_4 \sim N^+(5, 10^2)$ ;  $\zeta_t \sim N(0, 1)$ ;  $\delta_t \sim N(0, \tau^2)$ ; and  $\sigma^2, \tau^2, \lambda_t^2 \sim IG(0.5, 0.01)$ ; after rescaling the variables using the outcome-specific scaling factors presented in [Table 6](#). The baseline will be subtracted by the constant presented in [Table 6](#).

**Table 6 Constant to be subtracted from baseline, mean in the prior distributions of  $\alpha_1$  and  $\alpha_2$ , and scaling factor used in the Bayesian analyses**

Efficacy outcome	Constant to be subtracted from baseline	Mean $\bar{a}$ of the prior distributions of $\alpha_1$ and $\alpha_2$	Scaling factor
NUV	750 (mL)	-1	250 ( $\sim \frac{1}{4} L$ )
FUSP	180 (minutes)	1.5	60 ( $\sim 1$ hour)
NI Diary Total Score	50 (percentage points)	-2	10
NI Diary Overall Impact Score			( $\sim 10$ percentage points)

For each efficacy outcome, the posterior probability that FE 201836 performs better than placebo will be presented together with the difference to placebo with 95% credibility intervals for each dose of FE 201836.

Bayesian estimation of the sigmoidal dose-response curve for the aggregated responder variable corresponding to 50% reduction from baseline-RT in number of nocturnal voids,  $z_{50\%, 4, i}$ , will follow the primary analysis approach with imputed outcomes derived from the imputed values of  $y_{4, i}$  from the primary analysis. The dose-response model for  $z_{50\%, 4, i}$  will be modelled as a binary variable with mean

$$\text{Mean}(z_{50\%, 4, i}) = \text{expit}(( -0.5 \cdot x_{0, i} - \text{Mean}(y_{4, i}) ) / \text{SD}(y_{4, i}))$$

where  $\text{expit}$  is the function  $\text{expit}(x) = \exp(x)/(1+\exp(x))$ ,  $\text{Mean}(y_{4,i}) = \beta \cdot (x_{0,i} - 2) + \mu_d$ , and  $\text{SD}(y_{4,i}) = \sigma$  as specified in (1). The model parameters are modelled with the same prior distributions as used in the primary analysis. The posterior probability that FE 201836 performs better than placebo will be presented together with the odds ratio of at least 50% reduction from baseline-RT in number of nocturnal voids during 12 weeks of treatment for each dose of FE 201836 relative to placebo with 95% credibility intervals.

#### **10.3.4 Treatment effects on cross-sectional change from baseline for quantitative variables and PGI-I**

Treatment effects on cross-sectional change from baseline for quantitative variables will be analysed using SAS PROC MIXED assuming a MMRM (a non-parametric dose-response curve is assumed). The systematic effects will comprise visit number and treatment-by-visit as categorical variables, and the baseline-RT value as a linear covariate interacting with visit number. An unstructured covariance matrix will be used if technically possible, alternatively a Toeplitz, a compound-symmetry, or if necessary, an independent covariance matrix will be used. The treatment contrasts (with associated 95% confidence intervals without multiplicity adjustment) versus placebo will be tabulated and graphically illustrated. The analyses will be applied to the observed data on the ITT-RT analysis set.

The same approach will be applied to the aggregated average change from baseline in number of nocturnal voids.

For PGI-I there is no baseline so the systematic effects will comprise only visit number and treatment-by-visit as categorical variables.

